### **Risks to Research Participants**

There is minimum risk in alkalinizing local anesthetic solution. Sodium bicarbonate will be used as the exact FDA-approved purpose: to alkalinize acid solution. There may be additional risks of alkalinizing local anesthetic solution that are not known. However, numerous studies have published and no adverse effects have been reported. There is a risk of breach of confidentiality, which we plan to minimize this by de-identifying study data. There is a risk of less pain relief on one side of the mouth than the other due to one solution being less effective than the other.

### **Provisions to Protect the Privacy Interests of Research Participants**

Study recruitment and consent discussion will take place in private as is standard for a clinical appointment with a dentist. Study activities will take place in the privacy of the chairside of Tapper Dental Clinic or dental Clinic or Rainbow Center for Women and Children.

### **Potential Benefit to Research Participants**

There is a possibility of benefit with improved pain control on one side of the mouth, although this cannot be guaranteed. The findings of this study may benefit society in that they may help to demonstrate whether alkalinizing local anesthetics can anesthetize pediatric dental patients more effectively.

## **Withdrawal of Research Participants**

Participants could be withdrawn from study without their consent in the event of an error which renders the data yielded inaccurate (for example, monitor malfunction, recording not applied at correct time).

Should participants be withdrawn, their data will be kept but not utilized for the study. All information will be kept in a HIPPA protected file as if they had continued, all privacy maintained in regards to study data.

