## **Objectives**

The aim of this study is to compare physiological responses in children during the administration of buffered (with sodium bicarbonate) versus non-buffered local anesthetic (LA) control by recording and comparing changes in vital signs and physical movements in pediatric patients undergoing a dental procedure under deep sedation.

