## **Study Procedures**

I. All standard of care dental procedures will be followed for enrolled patients except as noted below:

1. IDS will dispense two types of local anesthetic solutionsto dental providers blindly: control solution (non-buffered LA, 2% lidocaine with epinephrine 1:100,000)) and test solution (buffered LA). Both types of solution will be administered to each subject. The types of solutions are labelled with numbers and the research team will remain blind to the type until the study is over.

2. The test solution will be made by a mixing pen called "Onset" (Onpharma Inc., Los Gatos, CA., USA), which is an FDA- approved device (see attachments). IDS will use a cartridge of 2% lidocaine with epinephrine 1:100,000 alkalinized at 9:1 ratio with a resulting pH of 7.21 using 8.4% sodium bicarbonate solution per manufacturer. This mixing pen Onset will deliver 0.18 mL of sodium bicarbonate solution into the anesthetic cartridge.

3. A dental provider will use a randomized coin flip to choose between the blindly labeled anesthetic agents to anesthetize one side of the mouth (left vs right). In addition, the sides of mouth will also be randomly selected by the toss of a coin. After the appropriate blind anesthetic solution has been selected, the same solution will be used to anesthetize each side of the mouth. In general, one cartridge of local anesthetic is sufficient to provide adequate anesthesia for 2 quadrants, however IDS will provide 2 cartridges of each solution in the event that a second cartridge of the same solution is needed. Maximum recommended dosage for local anesthetic will be calculated and followed for each patient. The provider will subsequently anesthetize the opposite side of the mouth with the opposite solution. The sequence used to administer the anesthetic will be inconsequential as the evaluation of pain will remain consistent due to the separation of nerve innervations in the posterior jaw.

4. Two researchers are required to present for each study. One researcher will be the provider who administrates LA and the other will be recording vital signs and physical movements during the injection (see point IV below).

II. In PSU, patients will be monitored per standard of care. This study does not cause potential interference with sedation monitoring.

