## **Provisions to Monitor the Data to Ensure the Safety of Research Participants**

As this is a pilot study and we are looking to enroll only 20 patients we will evaluate each patient after data has been collected to assure compliance with the protocol, and that the data set is complete and accurate. A bi-weekly team meeting will be held to discuss any safety events or issues.

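### One faulty reading can remove all of a child's data from both sides, on a discretionary judgement that may be made with the readings in view

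*Combined protocol and SAP*

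**What the plan says.** Withdrawal of Research Participants states that "Participants could be withdrawn from study without their consent in the event of an error which renders the data yielded inaccurate". It gives two examples: "for example, monitor malfunction, recording not applied at correct time". For a withdrawn child, "their data will be kept but not utilized for the study". The section gives no definition of an error, names no one to decide, and sets no time for the decision.

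Provisions to Monitor the Data to Ensure the Safety of Research Participants adds that "we will evaluate each patient after data has been collected to assure compliance with the protocol, and that the data set is complete and accurate".

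Three other statements bear on the point. The Objectives make the study one of "recording and comparing changes in vital signs and physical movements in pediatric patients", so movement is an outcome. Study Procedures says of the solutions that "Both types of solution will be administered to each subject", so a withdrawal takes out both halves of a within-child comparison. The same section says that "the research team will remain blind to the type until the study is over".

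The plan contains no rule for a reading missing at one event or on one side, no replacement rule, and no analysis that brings withdrawn children back in.

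**The concern.** The unit removed is larger than the unit at fault. A monitor failure or late entry affects one vital sign at one event on one side. The stated rule lets it remove every vital sign, movement record, pain score and sedation score from both sides, although most of these may be sound.

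The rule is also discretionary, and nothing prevents it from being applied once the values are known, because accuracy is checked after collection. If the chance of exclusion depends on how strongly the child responded, the children analysed are no longer the children enrolled, and the contrast between solutions can be distorted as well as less precise. With 20 children, a few withdrawals are enough to matter.

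**Working it through.** **Figures in the plan.** The plan gives 20 children, a significance level of 0.05 and independent t-tests. It gives no SD, effect size, power or expected withdrawal rate, so there is no stated figure to reproduce. What follows is an illustration on assumed inputs.

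**Assumptions.** Change scores on the two sides are bivariate normal with SD 1 and within-child correlation r of 0.3, 0.5 or 0.7. The true contrast (control minus buffered) is 0, 0.5 or 1.0 SD. Either 10% or 20% of children are withdrawn (2 or 4 of 20). Tests are two-sided. Power is for a paired t-test, because the design is split-mouth; the shrinkage figures for withdrawn children are mean within-child differences and do not depend on the choice of test.

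**Step 1. Cost per withdrawal.** 1/20 = 5% of the sample.

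**Step 2. Precision.** The SD of the within-child difference is √(2(1 − r)), which is √(2 × 0.5) = 1 at r = 0.5. The noncentrality is 0.5 × √n.
- n = 20: 0.5 × √20 = 2.24, power about 57%.
- n = 18: 0.5 × √18 = 2.12, power about 52%.
- n = 16: 0.5 × √16 = 2.00, power about 47%.

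**Step 3. When the contrast is unbiased** (1,000,000 simulated children per scenario).
- True contrast 0: it stays at 0.00 under every whole-child rule, and simulated 20-child trials give a type I error of about 5%.
- True contrast 0.5 SD, children dropped at random: it stays at 0.50.
- True contrast 0.5 SD, children dropped by the average of their two responses: it stays at 0.50.

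**Step 4. When it shrinks.** Children are dropped by the larger of their two responses, either strictly or in part (larger response plus equal noise). Shrinkage is 1 − remaining/true.

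| True contrast | Withdrawn | Rule | Remaining at r = 0.3 / 0.5 / 0.7 | Shrinkage |
|---|---|---|---|---|
| 0.5 | 10% | strict | 0.434 / 0.448 / 0.465 | 13.2% to 7.0% |
| 0.5 | 10% | partial | 0.456 / 0.465 / 0.475 | 8.8% to 5.0% |
| 0.5 | 20% | strict | 0.395 / 0.415 / 0.441 | 21.0% to 11.8% |
| 0.5 | 20% | partial | 0.426 / 0.442 / 0.459 | 14.8% to 8.2% |
| 1.0 | 10% | strict | 0.889 / 0.919 / 0.947 | 11.1% to 5.3% |
| 1.0 | 10% | partial | 0.925 / 0.943 / 0.964 | 7.5% to 3.6% |
| 1.0 | 20% | strict | 0.815 / 0.859 / 0.908 | 18.5% to 9.2% |
| 1.0 | 20% | partial | 0.874 / 0.904 / 0.937 | 12.6% to 6.3% |

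**Step 5. Both effects together.** In simulated trials of 20 children (true contrast 0.5 SD, r = 0.5), losing 4 at random gives power of about 47%, losing 4 partly by response about 42%, and losing the 4 largest responders about 41%. Of the 16-point fall from 57% to 41%, 10 points come from lost numbers and 6 from selection.

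**Step 6. A limit on any remedy.** If only the largest single readings are lost and the two sides are compared on whatever remains, a 0.5 SD contrast in that vital sign falls to about 0.36 with 10% of readings lost and about 0.30 with 20%. Keeping the child protects the other measures and events. It does not repair a vital sign whose loss depended on its own value.

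**The case against.** The strongest reply is that the listed grounds are equipment and operator errors. A reader might infer that a child who moves in pain is the one most likely to upset the monitor or the timing, so that the rule removes the strongest responders. The documents do not say this. They give no cause or rate for such errors, and recording movement is the second researcher's planned task, not a ground for withdrawal. The link is plausible, no more.

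A reader might also reach a much larger figure. Suppose movement occurs in 40% of control sides and 20% of buffered sides, independently, and a child who moves on either side is dropped with probability 0.75. The proportion retained is 0.6 × 0.8 + 0.52 × 0.25 = 0.61, and the 20-point difference becomes 0.20 × 0.25/0.61 = 8.2 points, a 59% reduction. The arithmetic is right, but none of the inputs has a source, it requires 39% of children to be withdrawn, and the Data Analysis Plan tests no proportion of children moving.

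Three further points stand. The team is blind to solution, which limits selection by solution (the plan does not say whether the number labels stay the same across children). Both sides leave together, so removing generally reactive children does not bias the contrast. The accuracy check does not mention withdrawal, so the two sections allow a decision after the readings are seen but do not prescribe one.

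None of this answers the main defect: one faulty reading can discard sound data from both sides, with no set criterion.

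**Conclusion.** The point holds as a defect in the exclusion rule, and it is worth correcting before enrolment. What rests on the text alone is that the rule is discretionary, removes the whole child, has no criterion or time point, and can be applied with the readings in view. Each use costs 5% of the sample.

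The loss of precision follows in every case; its size (57% to 47% paired power with 4 of 20 lost) rests on an assumed 0.5 SD contrast and correlation of 0.5. Bias toward zero needs two conditions that the documents do not establish: a true effect, and exclusion driven by the response on one side. If both hold, shrinkage at a 0.5 SD contrast is about 5% to 13% with 10% withdrawn and 8% to 21% with 20%. At 1.0 SD it is somewhat smaller, about 4% to 11% and 6% to 19%. The documents support neither a claim that the contrast will be biased nor a claim that a false positive would result.

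**What to change.** In Withdrawal of Research Participants:

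- Treat a faulty or mistimed reading as missing for that event and that measure only. Keep the child and all other valid vital signs, movement, pain and sedation scores. A pain or sedation score that was itself mistimed counts as faulty in the same way.
- Define recording errors objectively before the first child is enrolled.
- Record faults in a log during the case, and fix all exclusions, with reasons, before the solution code is opened.
- Report losses by solution and by reason.
- Analyse all children with available data. Where a vital sign is missing on one side, show the complete-pair result beside it, since step 6 of the working shows that the affected vital sign can remain biased.

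The cost is one fault-log line on the data collection sheet, some incomplete pairs, and a little more analysis work. Withdrawn children's data are already retained under the present rule, so no extra data collection is needed beyond the log.

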### **Number of Research Participants**

We will enroll 20 children who were patients of the Rainbow Babies and Children's Hospital's (RBC) Tapper Dental Clinic or Dental Clinic of Rainbow Center for Women and Children.

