III. The only additional device used in this study is Onset mixing system. The Onset device is already FDA-approved for pH buffering dental local anesthetic agents with sodium bicarbonate (see attachments).

IV. Data for this study will come from the EMR, the SDM, and intra-operative data collection sheets.

1. Vital signs, which are already recorded per standard of care at baseline and every 5 minutes, will be recorded manually for significant operative events by researchers on an intra-operative data collection sheet. Significant operative events includes: topical anesthesia, injection (needle puncturing the oral mucosal tissues), delivery of both buffered and conventional local anesthesia, surgical procedures (including tooth preparation, pulpal treatment, and tooth extractions). The necessity of additional local anesthesia delivery will also be noted.

2. Modified Behavioral Pain Scale (BPS) and Pediatric Sedation State Scale (PSSS) are valid and reliable tools in the assessment of pain in the unconscious sedated patient and monitor patient's comfort level during sedation, will be recorded on intra-operative data collection sheet by study personnel during the significant operative events as listed above. We removed the ventilation compliance in BPS form since this is not applicable in our study.

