### **Data Analysis Plan**

To assess compare the changes of vital signs, pain scores between buffered and conventional local anesthesia, we will use independent t-tests (SPSS v25). We considered a P-value of 0.05 or less significant.

The variability in measurements in this dental surgical population is currently unknown, therefore a power analysis is not appropriate. The data from this study will provide the necessary information to perform a power analysis for a future, larger trial.

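### A technical recording error can remove all of a child's data when only the affected readings need be dropped: a small, avoidable loss of precision in a 20-child pilot

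*Combined protocol and SAP*

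**What the plan says.** The rule is in Combined protocol and SAP, Withdrawal of Research Participants. A child may be withdrawn without consent "in the event of an error which renders the data yielded inaccurate (for example, monitor malfunction, recording not applied at correct time"). The consequence follows: "Should participants be withdrawn, their data will be kept but not utilized for the study". The wording is permissive: children could be withdrawn, not must be.

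Study Procedures describes several kinds of reading, taken at several operative events: topical anesthesia, needle puncture, delivery of each solution, and the surgical steps. On vital signs it says: "Vital signs, which are already recorded per standard of care at baseline and every 5 minutes"; researchers also write them down by hand at these events. The modified Behavioral Pain Scale (BPS) and the Pediatric Sedation State Scale (PSSS) "will be recorded on intra-operative data collection sheet by study personnel during the significant operative events as listed above". Each child receives both solutions, and "the research team will remain blind to the type until the study is over".

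The sample size is stated as "We will enroll 20 children who were patients of the Rainbow Babies" and a second clinic. The Data Analysis Plan compares "changes of vital signs, pain scores between buffered and conventional local anesthesia, we will use independent t-tests". It declines a power analysis because the variability is unknown, and adds: "The data from this study will provide the necessary information to perform a power analysis for a future, larger trial". It gives no rule for missing readings. The section on monitoring the data for safety has each child's data set checked after collection for compliance, completeness and accuracy, but does not mention withdrawal.

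**The concern.** The trigger and the consequence are on different scales. The trigger can be a fault in a single reading or a single instrument. The consequence covers every reading from that child, on both sides of the mouth, at every event and for every outcome. No section limits the exclusion to what was actually inaccurate.

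Two things are at stake. One is the precision of the comparison between solutions, where each child contributes to both arms. The other is the estimate of variability that the pilot is meant to pass on. With 20 children, neither has much to spare, and valid readings would be discarded for no gain.

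**Working it through.** **Inputs.** The number of children, 20, is from Number of Research Participants. The 0.05 significance level is from the Data Analysis Plan; it does not state sidedness, so two-sided 95% intervals are assumed. No SD, effect size, power or error rate is given, so there is no figure of the plan's own to reproduce. Results are in SD units, for one and two children removed. Two is an illustration, not a forecast.

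**1. Which readings each kind of error reaches**

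| Error in one child | Rule as written, if the child is withdrawn | If only affected readings are dropped |
|---|---|---|
| One mistimed recording, one side, one event | 19 children for every outcome and event | That reading is lost (20 v 19 in an independent t-test, 19 pairs if paired); 20 children at other events |
| Monitor fault throughout | 19 for every outcome and event | 19 for vital signs; 20 for BPS and PSSS |
| Faulty baseline vital signs | 19 for every outcome and event | 19 for vital-sign changes taken from that baseline; 20 for BPS and PSSS |

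The gain is therefore confined to outcomes and events that the error did not reach.

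**2. Planned independent t-test.** The 95% half-width in SD of the outcome, with n per solution, is t(0.975, 2n−2) × √(2/n).
- n = 20: 2.0244 × √(2/20) = 0.640
- n = 19: 2.0281 × √(2/19) = 0.658, ratio 1.028
- n = 18: 2.0322 × √(2/18) = 0.677, ratio 1.058

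**3. Within-child (paired) analysis, for comparison.** The 95% half-width in SD of the differences is t(0.975, n−1)/√n.
- n = 20: 2.0930/√20 = 0.468
- n = 19: 2.1009/√19 = 0.482, ratio 1.030
- n = 18: 2.1098/√18 = 0.497, ratio 1.063

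**4. Variability estimate for the later trial.** The upper 95% limit for the SD of the differences, as a multiple of the observed SD, is √((n−1)/χ²(0.025, n−1)).
- n = 20: √(19/8.907) = 1.461
- n = 19: √(18/8.231) = 1.479, ratio 1.012
- n = 18: √(17/7.564) = 1.499, ratio 1.026

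One child removed unnecessarily thus costs about 3% in interval width, whichever t-test is used, and about 1% in the upper limit for the SD.

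**The case against.** The strongest reply is that little may ever be lost. Withdrawal is optional, no error rate is given, and a sensible team might keep a child with one late recording. Some sheet errors might be recovered from the electronic record, although the 5-minute spacing limits this and a monitor fault could spoil both sources. The pilot makes no power claim, so a 3% wider interval changes no stated target. All of this stands, and it is why the point is minor. It does not remove the point, because a mistimed recording is one of the plan's own examples of a trigger, and the stated consequence is loss of the whole child.

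A second reply is that the scales are not always saved. One researcher records both vital signs and movements, and the scales go on the same sheet at the same events. A recording made at the wrong time may spoil both at that event. This also stands: BPS and PSSS are clearly saved only for monitor faults. After a mistimed recording, it is mainly the other events that are saved.

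A third reply is that the plan's blinding and its data check after each child would ordinarily settle errors before the code is broken. That is largely fair. The lack of a stated time window or exclusion log is missing detail rather than a fault in its own right.

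A reader might infer something stronger: that discretionary exclusion, made with readings in view, biases the comparison or shrinks the variance passed to the later trial. That would require exclusions to be related to outcome, for instance because movement disturbs the monitor. The documents do not say this, and any size put on it would rest on assumed withdrawal rates and assumed strengths of association. Blinding to solution, and removal of both sides of a child together, also limit bias towards either solution.

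**Conclusion.** The point holds as a minor one. The plan states a rule that can discard valid data, and a better rule is available at almost no cost. For outcomes and events untouched by the error, each child removed unnecessarily widens the 95% interval by 2.8% under the planned test or 3.0% if paired, and raises the upper limit for the SD of the differences by 1.2%. For the affected readings themselves there is no gain.

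The figures assume two-sided 95% intervals, an SD that does not change when a child is removed, and no replacement of withdrawn children. How often such an error would occur cannot be derived from the documents, so no expected total loss is given. Neither automatic loss of the child nor a biased comparison is established.

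**What to change.** Amend Withdrawal of Research Participants so that a technical error sets only the affected readings to missing. If the baseline vital signs are faulty, any vital-sign changes computed from them become missing too. Keep all other valid readings from that child in whatever analysis the Data Analysis Plan uses; the change does not depend on whether that analysis is paired. Make the decision while blind to solution, at the data check already planned after each child, and report the number of readings set to missing, with reasons.

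The cost is about one paragraph of protocol wording and a place on the data sheet to note the reading and the reason. No extra children or measurements are needed. The downside is that the number analysed will differ slightly across outcomes and events, so each result should show its own n. If the monitor fails throughout, or the baseline is faulty, the vital-sign readings or changes concerned are still lost.
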